# 4.5.4.6 Childhood depression inventory (CDI)

The Childhood Depression Inventory scale is a self-administrated 27-item questionnaire commonly used in research to assess depression. The short version 2 of 12 items is used in the study. The patient is asked to pick out the statement in each of the 12 items which best describes the way he feels right now at the moment of the assessment. The range of scores for the scale are 0-3 = none or minimal; 4-7 = mild; 8-15 = moderate;  $\geq 16 = \text{severe depression}$ .

## Analyses:

The CDI will be described, in terms of total score at baseline and at each post-baseline visit. It also described in term of range of scores.

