3.3.2. Secondary endpoints

As secondary endpoints the study will assess efficacy and safety endpoints in pitolisant and placebo groups:

- Changes in EDS as measured by the maintenance of wakefulness test (MWT) between baseline and V7,
- Changes in EDS measured by the Paediatric Daytime Sleepiness Scale (PDSS) between baseline: [V1 score (D-14) + V2 score (D0)]/2 and the end of treatment: [V6 score (D49) + V7 score (D56)]/2,
- Changes in EDS as measured by the Child and Adolescent Sleepiness Scale (CASS) between baseline and the end of treatment.
- Changes in the average number of cataplexy episodes per weeks: (recorded in sleep diary by patient and/or parent/teacher) between the 2 weeks of baseline and the 2 weeks of end study treatment period (V6, V7),
- Differences in weekly frequency of cataplexy episodes (recorded in sleep diary by patient and/or parent/teacher) between baseline and the 4 weeks of stable treatment period (V4 to V7),
- Severity of EDS measured by the clinical Global Impression of severity and change. Changes between baseline and V6, V7,
- Severity of cataplexy measured by the clinical Global Impression of severity and change. Changes between baseline and V6, V7,
- Changes between baseline and V6 will be compared for the TEA-Ch test,
- Comparison between placebo and pitolisant groups on:
 - Withdrawal symptoms questionnaire (DSM IV) on D59 during a phone call (T1) and at the end-of-study visit on D63 (V8) after a one-week period on placebo,
 - Patients' Global Opinion on treatment effect at the end of treatment if able to express

Protocol P11-06/ BF2.649 EudraCT number: 2013-001506-29

himself. If not will be reported either by parents or teachers.

- ,Tolerability as measured by Treatment Emergent Adverse Events (TEAE),
- Changes in Physical examination and Vital signs,
- ECG and calculation of Fridericia's corrected QTc interval (QTcF = $QT/\sqrt{3}\sqrt{60/HR}$),
- Blood laboratory tests (haematology, blood chemistry),
- Mood appraisal adapted to children (CDI and C-SSRS).
- Changes between baseline and at each visit of the open-label period in EDS,
- Safety assessment will be done on monitoring of adverse events, physical examination, vital signs, ECG and Blood Laboratory tests modifications and the mood appraisal throughout the study.

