3.4.2. Non inclusion criteria

- 1) Any other conditions that can be considered the primary causes of EDS: such as sleep related breathing disorders as defined by a sleep Apnea Index ≥ 5 per hour or/and an Apnea/Hypopnea Index ≥ 10 per hour, chronic sleep deprivation, circadian sleep wake rhythm disorder or any other medical or neurological causes that could account for narcolepsy symptoms associated with EDS.
- 2) Cataplectic patients treated by anticataplectics (SNRI, SSRI, sodium oxybate) which are not under a stable treatment since at least 4 weeks at the time of inclusion (V2).
- 3) Patients treated for cataplexy or any other pathology, by tricyclic antidepressants (clomipramine, imipramine, mirtazapine, desmethylimipramine and protriptyline) are not authorized because they display histamine H1 receptor antagonist activity.
- 4) The use of pitolisant within a 30-day period prior to initial screening visit (V0) for this trial.
- 5) Current or recent (within one year) history of a substance abuse or dependence disorder including alcohol abuse as defined in Diagnostic and Statistical Manual of Mental Disorders (DSM-IV).
- 6) Any significant abnormality of the electrocardiogram and particularly Fridericia's QTc interval (OTcF = $OT/3\sqrt{60/HR}$) higher than 450 ms.
- 7) Patients with severe depression (CDI \geq 16).
- 8) Patient with suicidal risk (C-SSRS).
- 9) Positive urinary drug testing (test applicable to patients from 12 years)

EudraCT number: 2013-001506-29

10) Pregnancy (defined as positive β-HCG blood test), breast-feeding, or patients and unable to use an efficient method of birth control shall not be included in the study (for pubescent female only).

- 11) Patients with severe hepatic Impairment (Child Pugh C) or with any other significant abnormality in the physical examination or clinical laboratory results.
- 12) Psychiatric and neurological disorders, such as moderate or severe psychosis or dementia, depression, history of seizure disorder or other problem that, in the investigator's opinion, would preclude the patient's participation and completion of this trial or comprise reliable representation of subjective symptoms.

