3.7.2.5. Childhood Depression Inventory

The Childhood Depression Inventory scale is a self-administrated 27-item questionnaire

commonly used in research to assess depression. The short version 2 of 12 items is used in the

study (Appendix 4). The patient is asked to pick out the statement in each of the 12 items which

best describes the way he feels right now at the moment of the assessment.

The range of scores for the scale are 0-4 = none or minimal; 4-7 = mild; 8-15 = moderate; ≥ 16

= severe depression.

The CDI questionnaire will be evaluated during double blind period at visits V1, V4, V6 and

V8 and all subsequent visits for the open-label period. Patients presenting severe depression

 $(CDI \ge 16)$ should be immediately withdrawn from the study for security.

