5.3.1. Criteria to withdraw subject from the trial treatment

In accordance with the Declaration of Helsinki, patients will be free to withdraw from the study at any time if they wish to do so, for any reason specified or unspecified.

Before the final scheduled study visit the investigator have the responsibility and the right to interrupt the patient participation. Out of emergency cases (listed below), the investigator will have to contact the sponsor or his representative before the application of his decision.

- Voluntary withdrawal of patient consent, or loss to follow-up, or inability to remain under medical observation
- Severe depression indicated by Childhood Depression Inventory (CDI \geq 16) or suicidal risk with a positive Columbia-Suicide Severity Rating Scale (C-SSRS).
- Non-compliance or major deviation from the protocol
- Appearance of a Serious Adverse Event (SAE) or any other situation where, in the opinion of the investigator, continuation of the study would not be in the interest of the subject.

Should any of the patients be withdrawn from the study, the reason for withdrawal has to be recorded in the CRF for all withdrawn patients.

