## 4.1.2 Descriptive statistics

Continuous variables will be described using: number of non-missing observations (N), number of missing observations (Nmiss), arithmetic mean (Mean), standard deviation (SD), minimum (MIN), quartile 1 (Q1), median (Median), quartile 3 (Q3) and maximum (MAX). MIN, Q1, Median, Q3 and MAX will be given at the data number of decimal points. Mean and SD will be given at 1 additional decimal point. 95% two-sided confidence interval (CI) will be calculated when appropriate using the standard method (Standard normal distribution).

Categorical variables will be presented using N, Nmiss and percentages (%). Missing data or unknown responses will not be included in the denominator for the calculation of percentages but will be presented in the results tables. Proportions will be displayed with one decimal.

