#### 4.1.4 Missing data

#### 4.1.4.1 General considerations

(ICH E3; 9.7.1, 11.4.2.2. ICH E9; 5.3. EMA Guideline on Missing Data in Confirmatory Clinical Trials) Missing data will be imputed for five main endpoints of this study (UNS, PDSS, UNS-CTP, WRC and MWT). For the other endpoints no missing value will be imputed.

A Multiple Imputation (MI) procedure will be used to impute the missing evaluations, as a prior step, assuming that those patients would be in their randomized arm. The partially complete datasets will be generated with a model including the following covariates age, gender and the main model components (section 2.2).

A total of 100 imputed partially complete datasets will be generated.

MI inference involves 3 consecutives phases:

- 1/ Imputation step:

The missing pattern is supposed to be monotone, so the regression method will be used to impute missing data.

The partially complete datasets will be generated with a model including age, gender factors and taking into account the baseline score of the primary endpoint, based on patient which every postbaseline measurement available. It is of note that this imputation step might be preceded by one MI approach based on MCMC method, in case of arbitrary missing pattern. A total of 100 imputed partially-complete datasets will be generated.

The mean MD imputation will based on Missing at Random (MAR) corresponding to the hypothesis that missingness is assumed independent of the outcome, or to estimate a "de jure" (per protocol) estimand, censoring after any protocol deviation. This hypothesis was considered as the most likely in this particular context.

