## Analyses

The CDI will be described, in terms of Suicidal risk (Yes/No) at baseline and at each post-baseline visit.

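### The SAP tabulates CDI and C-SSRS visit by visit, with no visible once-per-child count or listing of children who ever reach CDI ≥ 16 or a positive C-SSRS after baseline

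*SAP*

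**What the plan says.** Protocol 3.3.2 names the CDI and the C-SSRS among the secondary endpoints, as mood appraisal. Protocol 3.4.2 excludes children with CDI ≥ 16 or suicidal risk at entry, so a positive result after baseline in an eligible child is new.

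The protocol then acts on a positive result, in two strengths of wording:
- CDI ≥ 16 (Protocol 3.7.2.5): such children "should be immediately withdrawn from the study for security".
- C-SSRS (Protocol 5.3.1): the list of reasons for which the investigator may end participation includes "suicidal risk with a positive Columbia-Suicide Severity Rating Scale (C-SSRS").

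For the analysis, SAP 4.5.4.6 states: "The CDI will be described, in terms of total score at baseline and at each post-baseline visit". It adds a description by score range, without naming a time point. SAP 4.5.4.7 describes the result "in terms of Suicidal risk (Yes/No) at baseline and at each post-baseline visit". That sentence names the CDI, but it stands in the C-SSRS section and plainly means the C-SSRS.

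On missing values, SAP 4.1.4.1 limits imputation to five efficacy endpoints: "For the other endpoints no missing value will be imputed". SAP 4.1.2 states: "Missing data or unknown responses will not be included in the denominator for the calculation of percentages". The same sentence goes on to say that missing data will be shown in the results tables, and the number missing is a standard column.

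Neither 4.5.4.6 nor 4.5.4.7 defines a worst post-baseline value, a shift from baseline, an any-time count or a listing.

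**The concern.** The safety question for these scales is how many treated children in each arm ever crossed the threshold. A by-visit table answers a different one: how many of the children assessed at this visit are positive now. For most safety measures the two stay close. Here a positive result is itself a reason to leave, so positive children tend to disappear from the later rows.

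The SAP already uses patient-level presentations for comparable data. Section 4.5.4.1 counts patients with at least one adverse event, 4.5.4.3 lists patients with a clinically significant laboratory abnormality, and 4.5.4.5 lists patients with a clinically significant ECG value at any time after dosing. The two mood scales get no such summary in the visible text. What is at stake is how clearly a paediatric mood signal would be reported, not a test result.

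**Working it through.** The documents give no CDI or C-SSRS rate, so there is no figure to reproduce and the case numbers below are assumed.

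**Inputs**
- Planned arms: 72 pitolisant, 36 placebo (SAP 4.2).
- CDI after baseline: V4, V6 and V8, which is 3 visits. C-SSRS after baseline: V3 to V8, which is 6 visits. Both scales are repeated at the premature-withdrawal visit (SAP Table 1).

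**Case A: every positive child leaves at once, no other drop-out, withdrawal visit not tabulated.** Active arm, one new C-SSRS case at each of V3 to V7:

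| Visit | V3 | V4 | V5 | V6 | V7 | V8 |
|---|---|---|---|---|---|---|
| Positive / assessed | 1/72 | 1/71 | 1/70 | 1/69 | 1/68 | 0/67 |
| % | 1.4 | 1.4 | 1.4 | 1.4 | 1.5 | 0 |

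Sum of counts = 5, and 5/72 = 6.9% were ever positive. For the CDI, one case at V4 and one at V6 give 1/72, 1/71 and 0/70. The sum is 2, and 2/72 = 2.8%. In this case the reader can recover the incidence by adding the numerators.

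**Case B: some positive children stay.** From visit counts c₁…c_k alone, the number ever positive lies between max(c_j) and min(N, Σc_j). With one positive at every post-baseline visit:

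| Scale | Children ever positive | % of 72 | % of 36 |
|---|---|---|---|
| CDI (k = 3) | 1 to 3 | 1.4 to 4.2 | 2.8 to 8.3 |
| C-SSRS (k = 6) | 1 to 6 | 1.4 to 8.3 | 2.8 to 16.7 |

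The number missing at each visit helps to tell one repeat case from several leavers only while there is no other drop-out.

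**Case C: the withdrawal visit is tabulated as well.** Protocol 5.2.10 puts V8 and the premature-withdrawal visit under one heading, and the SAP does not say which row the withdrawal values enter. Suppose that all five children of Case A are again positive at a separate withdrawal visit and those values go into the V8 row. The counts then sum to 5 + 5 = 10 for 5 children. Conversely, if withdrawal and unscheduled values are left out, a child first positive at such a visit appears in no row and the sum is too small.

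The visit rows therefore give the per-arm incidence only under Case A, and the SAP text does not ensure Case A.

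**The case against.** The strongest reply is that little is lost. If positive children leave, each is counted once and the numerators add up. If they stay, they also stay in the denominator. Missing values are displayed beside the percentages. The adverse-event route is substantial. The definition in Protocol 6.1.5.1 covers clinically relevant results that lead to withdrawal. SAP 4.5.4.1 plans patient counts of treatment-emergent events, including those that lead to stopping the drug, and a listing of all events. SAP 4.5.1.1 tabulates reasons for withdrawal. Finally, the table shells are a separate file (SAP sections 5 and 6) and may contain the count. The list of special-interest terms does not appear in the available text either.

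Most of this stands, and it rules out several stronger readings:
- A reader might infer from Case A that the tables turn 6.9% into 1.5%. That sets one row against a cumulative total, which no by-visit table claims to show.
- A reader might infer that missing children vanish unseen. SAP 4.1.2 says that they are shown.
- A reader might infer that withdrawal is mandatory for both scales. The immediate wording applies to the CDI; for the C-SSRS it is a criterion under the investigator's responsibility.
- A reader might infer that a mood signal would go unreported. The adverse-event and disposition tables should show much of it.

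What the reply does not remove is narrower. Adverse-event tables count coded terms, not scale thresholds. Disposition is by randomised arm in the randomised and full analysis sets, while safety is by actual arm in the Safety Set. The softer C-SSRS rule and the unstated handling of the withdrawal visit are also why the visit counts need not equal the number of children.

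**Conclusion.** The point holds as an optional improvement in safety reporting. No visible scale-based table or listing gives the number of children per arm who ever reach CDI ≥ 16 or a positive C-SSRS after baseline, and the by-visit rows yield it only if every positive child leaves at once and withdrawal values are not counted again.

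Its size cannot be derived, because the documents give no rates. The ranges above (for example 1 to 6 children of 72 for the same six C-SSRS counts) rest on assumed cases and planned arm sizes, with no drug effect implied. No inferential result changes. The documents do not show that the count is absent from the trial's outputs, since the shells cannot be seen. The naming of the CDI in the C-SSRS section is clerical.

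**What to change.** In SAP 4.5.4.6 and 4.5.4.7 add, by actual arm in the Safety Set:
- the number and percentage of treated children with any post-baseline CDI ≥ 16;
- the number and percentage with any post-baseline positive C-SSRS;
- a case listing, as already planned for ECG.

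Count each child once, through V8, and include premature-withdrawal and unscheduled visits. Say in one sentence which row of the by-visit tables takes the withdrawal-visit values. Keep the by-visit tables, and correct CDI to C-SSRS in 4.5.4.7.

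The cost is SAP wording, one summary table and one listing from data already collected. If the shells already contain these, a sentence in the SAP pointing to them is enough.

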# 4.5.4.7 Columbia-suicide severity rating scale (C-SSR)

The Columbia-Suicide Severity Rating Scale (C-SSRS) will be evaluated at all visits of the study. This scale is intended to be used by individuals who have received training in its administration. The questions contained in the C-SSRS are suggested probes. Ultimately, the determination of the presence of suicidal ideation or behavior depends on the judgment of the individual administering the scale. The interview is semi-structured with a flexible format. Questions are provided as helpful tools – it is not required to ask any or all questions – just enough to get the appropriate answer. Most important: gather enough clinical information to determine whether patient is suicidal or not. If it is established that a patient has not engaged in any suicidal behavior and/or ideation, then no further questions are required.

## Analyses

The CDI will be described, in terms of Suicidal risk (Yes/No) at baseline and at each post-baseline visit.

# 4.6 Modifications from the statistical section of the protocol

Not Applicable.

## 4.7 Interim analysis

Not Applicable.

## 5 Tables, Listings and Graphs (TLG)

BIOPROJET\_P11-06\_Mock\_UP\_TFLs\_FinalVersion\_V1.0.pdf

## 6 Template of tables, listings and graphs

BIOPROJET\_P11-06\_Mock\_UP\_TFLs\_FinalVersion\_V1.0.pdf

